9.5. Safety Analysis

Safety analysis will be performed for PK Lead-in Phase and for Treatment Phase respectively. Safety data will be summarized by age group and overall for PK Lead-in Phase and by treatment regimen for each age group for the Treatment Phase.

Safety will be evaluated by assessment of clinical laboratory tests, physical examinations, vital signs measurements, and by the documentation of AEs.

All safety data collected while on or after the first dose of study drug administration up to 30 days after the last dose of study drug will be summarized according to the study drug received.

Safety endpoints will be analyzed by the number and percent of subjects with events or abnormalities for categorical values or 8-number summary (n, mean, standard deviation, median, Q1, Q3, minimum, maximum) for continuous data.

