1.3. Ribavirin (RBV)

Ribavirin is a guanosine analogue that inhibits the in vitro replication of a wide range of RNA and DNA viruses {Roche Laboratories Inc. 2010, Roche Products Limited 2010}. Ribavirin monotherapy has little or no effect on the replication of HCV but can result in normalization of serum ALT activity and improvement in liver histology. When combined with interferon or PEG therapy, RBV decreases substantially the relapse rate seen after cessation of interferon therapy {McHutchison 1998, Poynard 1998}.

Ribavirin is a known teratogen (FDA category X). Furthermore, RBV is known to accumulate intracellularly where it is cleared slowly, and is also excreted in semen. Therefore, extreme care must be taken to avoid pregnancy during RBV therapy and for up to 7 months following completion of treatment. A comprehensive review of RBV is contained in the package insert/SmPC.

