8.2.2. Assessment of Severity

The severity grading of AEs will be assessed as Grade 1, 2, 3, or 4 using the GSI Grading Scale for Severity of Adverse Events and Laboratory Abnormalities ([Appendix 3](#)).

For AEs associated with laboratory abnormalities, the event should be graded on the basis of the clinical severity in the context of the underlying conditions; this may or may not be in agreement with the grading of the laboratory abnormality.

8.3. Investigator Requirements and Instructions for Reporting Adverse Events and Serious Adverse Events to Gilead or CRO

Requirements for collection prior to study drug initiation:

After informed consent, but prior to initiation of study medication, the following types of events should be reported on the case report form (CRF/eCRF): all SAEs and adverse events related to protocol-mandated procedures.

Adverse Events

Following initiation of study medication, collect all AEs, regardless of cause or relationship, until 4 weeks after last administration of study drug must be reported to the CRF/eCRF database as instructed.

All AEs should be followed up until resolution or until the adverse event is stable, if possible. Gilead Sciences may request that certain AEs be followed beyond the protocol defined follow up period.

Serious Adverse Events

All SAEs, regardless of causal relationship, that occurs after the subject first consents to participate in the study (i.e., signing the informed consent) and throughout the duration of the study, including the protocol-required 24-week post treatment follow-up period, must be reported to the CRF/eCRF database and Gilead Drug Safety and Public Health (DSPH) as instructed. This also includes any SAEs resulting from protocol-mandated procedures performed after informed consent is signed.

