Appendix Table 3. Treatment Phase: Post Treatment Visits Following Primary Study

	4 Weeks Post Treatment	12 Weeks Post Treatment	24 Weeks Post Treatment
Clinical Assessments			
Vital Signs, Body weight and Height	X	X	X
Symptom-directed Physical Exam	X	X	X
AEs	X	X ^c	X ^c
Concomitant Medications	X		
Quality of Life Survey ^a		X	X
Tanner Pubertal Stage Assessment		X	X
Bone Age Assessment			X
Pregnancy Prevention Counseling ^d	X	X ^f	X ^f
Laboratory Assessments			
Hematology, Chemistry	X	X	
HCV RNA	X	X	X
Viral Sequencing ^b	X	X	X
Urine Pregnancy Test	X	X ^c	X ^c
HBV DNA ^g	X	X	X

a Quality of life survey will be completed by all subjects at 12-Week and 24-Week Post Treatment visits if a site is approved to use the survey. Subject is to review questionnaire with a parent/guardian and write/mark answers directly onto the questionnaire.

b Plasma samples will be collected and stored for potential HCV sequencing and other virology studies

c At Post Treatment Week 12 and 24, only SAEs will be captured

d Including partner pregnancy prevention for male participants (all subjects \geq 12 years of age and subjects < 12 years of age at the discretion of the Investigator based on subject's pubertal status).

e GT-3 subjects only: Female subjects of childbearing potential should be provided with Urine Pregnancy Test Kits, instructed on their use and requested to continue to self-monitor for pregnancy for 6 months after their last dose of RBV. If required by regulations, additional pregnancy tests beyond 6 months may be added. The subject should be contacted every 4 weeks and asked to report results of the urine pregnancy tests. If a positive urine pregnancy test is reported, the subject should return to the clinic for a serum pregnancy test.

f GT-3 subjects only

g Only subjects HBcAb positive at Screening

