7.1.6. Summaries of Adverse Events and Deaths

A brief high-level summary of TEAEs will be provided by treatment group and by the number and percentage of subjects who had the following: any AE; any AE of Grade 3 or above; any AE of Grade 2 or above; any treatment-related AE; any treatment-related AE of Grade 3 or above; any treatment-related AE of Grade 2 or above; any SAE; any treatment-related SAE; any AE that led to premature discontinuation of any study drug; any AE that led to premature discontinuation of all study drugs; any AE that led to premature discontinuation of LDV/SOF FDC; any AE that led to premature discontinuation of RBV; any AE that led to modification or interruption of any study drug; any AE that led to interruption of LDV/SOF FDC; any AE that led to modification or interruption of RBV. All deaths (including those that are treatment emergent and those that are not treatment emergent) observed during the study will also be summarized and included in this table. Additionally, for subjects 3 to < 6 years of age, a brief high-level summary of TEAEs will be provided by treatment group defined [Table 3-3](#).

Adverse event summaries will provide the number and percentage of subjects with TEAEs by SOC and PT, by treatment group based on the Safety Analysis Set as follows:

- All AEs
- AEs of Grade 3 or above
- AEs of Grade 2 or above
- All treatment-related AEs
- Treatment-related AEs of Grade 3 or above
- Treatment-related AEs of Grade 2 or above
- All SAEs

- All treatment-related SAEs
- AEs leading to premature discontinuation of any study drug
- AEs leading to premature discontinuation of all study drugs
- AEs leading to premature discontinuation of LDV/SOF FDC
- AEs leading to premature discontinuation of RBV
- AEs leading to modification or interruption of any study drug
- AEs leading to interruption of LDV/SOF FDC
- AEs leading to modification or interruption of RBV

Multiple events will be counted only once per subject in each summary. Adverse events will be summarized and listed first in alphabetic order of SOC and then by PT in order of descending incidence of the pooled treatment groups within each SOC. In summaries by severity grade, the most severe grade will be used for those AEs that occurred more than once in an individual subject during the study.

In addition to the above summary tables, TEAEs will be summarized by PT only, in order of descending incidence within the pooled treatment groups for:

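### SAEs are collected to post-treatment Week 24, but the SAE rows and tables count only treatment-emergent events, so later SAEs enter no count or percentage although later deaths do

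*Protocol*

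**What the plan says.** **Collection.** Protocol 8.3 requires that SAEs arising after consent and "throughout the duration of the study, including the protocol-required 24-week post treatment follow-up period, must be reported to the CRF/eCRF database", irrespective of causality. Other adverse events are collected only "until 4 weeks after last administration of study drug must be reported". Protocol Appendix Table 3 confirms the split in a footnote: "At Post Treatment Week 12 and 24, only SAEs will be captured".

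**Analysis.** Protocol 9.5 says what will be summarised: "All safety data collected while on or after the first dose of study drug administration up to 30 days after the last dose". Protocol 9.5.2 puts its SAE and treatment-related SAE tables under the heading of treatment-emergent events. SAP 7.1.5.1 defines these as events starting between first dose and 30 days after permanent discontinuation, plus any event that led to premature discontinuation. SAP 7.1.6 applies that definition in three places:

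- the high-level summary;
- the tables by system organ class and preferred term: "Adverse event summaries will provide the number and percentage of subjects with TEAEs by SOC and PT";
- the preferred-term-only tables.

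**Deaths.** The same high-level table treats deaths differently: "All deaths (including those that are treatment emergent and those that are not treatment emergent) observed during the study will also be summarized".

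**Listings.** Protocol 9.5.2 lists every adverse event collected. SAP 7.1.6 plans a listing of all adverse events with a treatment-emergent indicator, and separate listings of SAEs and of deaths.

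**The concern.** After the 4-week post-treatment visit, SAEs are the only adverse events still being collected, and no planned summary uses the ones that start more than 30 days after the last dose. A reader who sees a row called 'any SAE' or 'any treatment-related SAE' may take it to cover the period over which SAEs were gathered. It does not, and an investigator's judgement that a late event is related does not bring it in.

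Safety and tolerability are the primary objective of the Treatment Phase. The SAE rows could show zero while the listings hold one or more late events. One table could also use two time bases without saying so, one for deaths and another for SAEs.

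**Working it through.** **Inputs**

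- Post-treatment follow-up: 24 weeks = 168 days (Protocol 3.2.2 and 8.3).
- Treatment: 12 weeks = 84 days, or 24 weeks = 168 days (Protocol 3.2.2).
- Treatment-emergent limit: 30 days after the last dose (Protocol 9.5 and 9.5.2; SAP 7.1.5.1).
- Planned size: about 100 adolescents and 120 children, 220 in total (Protocol 3.1.2 and 4.1).

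**The plan's own figure.** Protocol 3.2.2 gives a total of about 40 or 52 weeks. Screening + treatment + follow-up gives 4 + 12 + 24 = 40 and 4 + 24 + 24 = 52, so the 24-week follow-up is confirmed. The documents state no SAE rate to reproduce.

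**Collection time outside the SAE tables**

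- Post-treatment days left out: 168 − 30 = 138.
- Share of post-treatment collection: 138/168 = 82%. With the ±5-day visit tolerance it is 133/163 = 82% to 143/173 = 83%.
- Share of time from first dose, 12-week regimen: 138/(84 + 168) = 138/252 = 55%.
- Share of time from first dose, 24-week regimen: 138/(168 + 168) = 138/336 = 41%.
- Person-time, if all 220 complete follow-up: 220 × 138/365.25 = 83 subject-years.

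**How single events would be handled** (complete onset date, drug not stopped because of the event)

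| SAE onset after last dose | Collected | SAE rows and tables | Deaths row | Listings |
|---|---|---|---|---|
| Day 20, non-fatal | yes | counted | – | yes |
| Day 60, non-fatal, related or not | yes | not counted | – | yes |
| Day 60, fatal | yes | not counted | counted | yes |

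**Exceptions.** An event that led to premature discontinuation is treatment-emergent whenever it starts, but one that begins more than 30 days after the last dose cannot normally be the reason for stopping. The incomplete-date rules in SAP 7.1.5.2 work by month and year, so they could let in an occasional event that began after day 30.

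**Effect of one late event.** If a row would otherwise read zero, one newly counted subject makes it 1/220 = 0.45% overall, 1/100 = 1.0% in adolescents or 1/120 = 0.83% in children.

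**The case against.** The strongest reply is that this is a choice of presentation and not an inconsistency.

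- **The window is applied consistently.** Protocol 9.2.1.2, 9.5 and 9.5.2 and SAP 7.1.5.1 all use 30 days. Because non-serious events are collected for only 4 weeks after treatment, the limit keeps all treatment-emergent rows on almost the same time base. This stands, and it is why the 30-day rows should stay as they are.
- **Late SAEs are visible.** They are listed with a flag, and for a handful of events a listing may tell more than a percentage. During the study they also reach the sponsor's safety unit within 24 hours (Protocol 8.3), and a data monitoring committee reviews safety. A reader might infer that late SAEs are lost. They are not. What is missing is a count by treatment group.
- **The primary endpoint is untouched.** Protocol 9.1.2 defines it as an adverse event that causes permanent discontinuation of study drug, and the treatment-emergent definition includes such events without a time limit. A reader might infer that the primary safety result is biased, and nothing in the documents supports that.
- **The deaths row sets no rule.** Summarising all deaths does not oblige the sponsor to do the same for SAEs. That is fair. It does show that the sponsor accepts a whole-study row in this table, and SAP 7.4, 7.6 and 7.7 also carry growth, bone age and Tanner stage to post-treatment Week 24.
- **Ribavirin does not strengthen the point.** A reader might infer a particular late risk from the statement that "RBV is known to accumulate intracellularly where it is cleared slowly". In Protocol 1.3 that statement leads to advice on avoiding pregnancy, and pregnancies have their own reporting route and listing. Ribavirin is also given only to GT-3 subjects, who appear in SAP Table 3-1 as one group aged 6 to under 12 years.

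**Conclusion.** The point holds as an inexpensive reporting improvement, not as an error in the treatment-emergent definition. SAEs that start more than 30 days after the last dose, including any judged related, contribute to no planned count or percentage, while deaths over the same period do.

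The size that can be stated is calendar time: 82% of post-treatment SAE collection, or about 83 subject-years. The latter assumes that all of about 220 subjects complete 24 weeks of follow-up, so dropout would lower it. These are shares of time and not of events, and all of the omitted time is off drug, so they should not be read as the share of safety information lost.

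It is tempting to multiply the 83 subject-years by a background SAE rate to get an expected number of uncounted events. The documents give no such rate, and an all-cause rate would say nothing about related SAEs. If no late SAE occurs, the two new rows will equal the treatment-emergent ones and no conclusion changes.

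**What to change.** In the SAP only, add two rows by treatment group to the 7.1.6 high-level table, beside the treatment-emergent rows and on the Safety Analysis Set:

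- any SAE from first dose to end of study;
- any treatment-related SAE from first dose to end of study.

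End of study is the 24-week post-treatment visit. The existing rule in SAP 7.1.3 that counts missing causality as related can apply unchanged. The 30-day definition and all existing rows and tables stay.

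No new data or visit is needed, since the events are already collected and listed. Protocol 9.5.2 need not be edited, which avoids the ethics and regulatory submission required under Protocol 10.2.1. SAP 7.10 should record the addition in one line. If the SAP is already final, the change is documented in the clinical study report, as SAP section 1 provides.

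The downside is that late unrelated SAEs will also appear. Separate, clearly labelled rows keep them out of the treatment-emergent rates.

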9.5.1. Extent of Exposure

A subject's extent of exposure to study drug will be generated from the study drug administration page of the CRF. Exposure data will be summarized.

9.5.2. Adverse Events

Clinical and laboratory AEs will be coded using the Medical Dictionary for Regulatory Activities (MedDRA). System Organ Class (SOC), High-Level Group Term (HLGT), High-Level Term (HLT), Preferred Term (PT), and Lower-Level Term (LLT) will be attached to the clinical database.

Events will be summarized on the basis of the date of onset for the event. A treatment-emergent adverse event will be defined as any adverse event with an onset date on or after the study drug start date and no later than 30 days after permanent discontinuation of the study drug or any adverse event leading to premature discontinuation of the study drug.

Summaries (number and percentage of subjects) of treatment-emergent adverse events (by SOC and preferred term) will be provided by cohort:

- All AEs,
- All treatment-related AEs,
- Combined Grade 2, 3 and 4 AEs,
- Combined Grade 3 and 4 AEs,
- Combined Grade 2, 3 and 4 treatment-related AEs,
- Combined Grade 3 and 4 treatment-related AEs,
- All AEs that caused permanent discontinuation from study drug,
- All AEs that caused change in dose or temporary interruption of study drug,
- All SAEs,
- All treatment-related SAEs

All AEs collected during the course of the study will be presented in data listings.

9.5.3. Laboratory Evaluations

Selected laboratory data will be summarized using only observed data. Absolute values and changes from baseline at all scheduled visits will be summarized. Graded laboratory abnormalities will be defined using the grading scheme in Grading of Laboratory Abnormalities provided in [Appendix 3](#). Incidence of treatment-emergent laboratory abnormalities, defined as values that increase by at least one toxicity grade from baseline at any time post baseline up to and including the date of last dose of study drug plus 30 days, will be summarized by age group and overall. If baseline data are missing, then any graded abnormality (i.e., at least a Grade 1) will be considered treatment emergent.

All laboratory abnormalities will be included in the listings of laboratory data.

9.5.4. Other Safety Evaluations

9.5.4.1. Tanner Pubertal Stage Assessment

Tanner Stages ([Appendix 4](#)) will be summarized by baseline Tanner Stage using frequency and percentage.

9.5.4.2. Vital Signs (including Body Weight and Height)

Vital signs including body weight and height and change from baseline will be summarized at each visit.

9.6. Efficacy Analysis

Efficacy will be evaluated using scheduled assessments of HCV RNA performed using COBAS[®] TaqMan[®] HCV Test, v2.0 for use with the High Pure System.

Efficacy analysis will be performed by treatment regimen for each age group for Treatment Phase.

All continuous endpoints will be summarized using an 8-number summary (n, mean, standard deviation, median, Q1, Q3, minimum, maximum). All categorical endpoints will be summarized by number and percentage of subjects who meet the endpoint definition.

9.6.1. Key Efficacy Analysis

The key efficacy endpoint is SVR12 (HCV RNA < LLOQ 12 weeks after completion of treatment) in the FAS population. Point estimate and its 95% confidence interval will be provided.

9.6.2. Secondary Efficacy Analysis

For the PK Lead-in Phase, serum HCV RNA actual values and change from baseline will be summarized at each visit.

For the Treatment Phase, the proportion of subjects with HCV RNA below LLOQ over time (including SVR endpoints SVR4 and SVR24) will be presented in tabular and graphical form. In addition, descriptive summaries and listings will be provided for additional efficacy evaluations including serum HCV RNA actual values and change from baseline, proportion of subjects with virologic failures, and other endpoints of interest including ALT normalization.

PPD

9.6.3. Subgroup Analysis

Subgroup analysis on SVR12 will be performed by treatment experience and cirrhosis status, by IL28B genotype, and by HCV genotype. Other clinically relevant subgroup analyses may be conducted as appropriate (i.e., assuming that adequate numbers of subjects in these subsets are available for analysis).

Details on efficacy analyses will be described in the statistical analysis plan.

9.7. Quality of Life Analysis

The data from PedsQL™ Pediatric Quality of Life survey will be summarized by visit and age group and overall.

9.8. Acceptability

Acceptability of the study treatments will be summarized using descriptive statistics by assessing swallowability of the solid dosage tablet formulations (if subject is able to swallow the tablet) and evaluating palatability of the granules formulation as applicable.

9.9. Data Monitoring Committee

An external multidisciplinary data monitoring committee (DMC) will review the progress of the study and perform interim reviews of safety and provide recommendation to Gilead about whether the nature, frequency, and severity of adverse effects associated with study treatment warrant the early termination of the study in the best interests of the participants, whether the study should continue as planned, or the study should continue with modifications.

The DMC's specific activities will be defined by a mutually agreed charter, which will define the DMC's membership, conduct and meeting schedule.

While the DMC will be asked to advise Gilead regarding future conduct of the study, including possible early study termination, Gilead retains final decision-making authority on all aspects of the study.

9.10. Sample Size

With approximately 100 subjects enrolled into 12 to <18 years (Group 1) of the Treatment Phase, a two-sided 95.0% confidence interval of the SVR12 rate will extend at most 5.9% in both directions from the observed SVR12 rate, assuming the expected SVR12 rate is 90%.

With approximately 120 subjects enrolled into the 3 to < 12 years (Group 2) of the Treatment Phase, a two-sided 95.0% confidence interval of the SVR12 rate will extend at most 5.4% in both directions from the observed SVR12 rate, assuming the expected SVR12 rate is 90%.

10. RESPONSIBILITIES

10.1. Investigator Responsibilities

10.1.1. Good Clinical Practice

The investigator will ensure that this study is conducted in accordance with the principles of the “Declaration of Helsinki” (as amended in Edinburgh, Tokyo, Venice, Hong Kong, and South Africa), International Conference on Harmonization (ICH) guidelines, or with the laws and regulations of the country in which the research is conducted, whichever affords the greater protection to the study subject. For studies conducted under a United States IND, the investigator will ensure that the basic principles of “Good Clinical Practice,” as outlined in 21 CFR 312, subpart D, “Responsibilities of Sponsors and Investigators,” 21 CFR, part 50, 1998, and 21 CFR, part 56, 1998, are adhered to.

Since this is a “covered” clinical trial, the investigator will ensure that 21 CFR, Part 54, 1998, is adhered to; a “covered” clinical trial is any “study of a drug or device in humans submitted in a marketing application or reclassification petition subject to this part that the applicant or FDA relies on to establish that the product is effective (including studies that show equivalence to an effective product) or that make a significant contribution to the demonstration of safety.” This requires that investigators and all sub-investigators must provide documentation of their financial interest or arrangements with Gilead Sciences, or proprietary interests in the drug being studied. This documentation must be provided before participation of the investigator and any sub-investigator. The investigator and sub-investigator agree to notify Gilead Sciences of any change to reportable interests during the study and for one year following completion of the study. Study completion is defined as the date that the last subject has completed the protocol defined activities.

This study is also subject to and will be conducted in accordance with 21 CFR, part 320, 1993, “Retention of Bioavailability and Bioequivalence Testing Samples.”

